Several RCT have shown that hypoglycemia occurs in 12% and 33% of general medicine and surgery patients treated with basal bolus insulin regimens, respectively (6; 7; 11; 12). In the RABBIT-surgery trial (6), general surgery patients were treated with a total insulin dose of 0.5 unit/kg/day, given half as glargine once daily and half as glulisine before meals. A total of 17% of patients had a BG <70 mg/dL and 4% had a value <40 mg/dL. More recently, the Basal Plus trial (11) reported that 12% and 5% of patients treated with basal bolus with glargine and glulisine or with basal plus correction (supplements), respectively, had a BG <70 mg/dL and

only 1% had a BG <40 mg/dL. In the DEAN trial (12), a basal-bolus regimen using detemir and aspart vs. NPH and regular insulin reported that ~one-third of patients had a BG < 60 mg/dl (12). Minimizing hypoglycemic events is of major importance in hospitalized patients because it has been shown to be an independent risk factor of poor outcome (23-25). It is not known, however, if the use of insulin supplements may have an impact on the overall rate of hypoglycemia in patients treated with basal bolus insulin regimen.

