##### **IV.b. Primary and Secondary Outcomes:**

The primary outcome of the study is to compare differences in mean daily BG levels between patients receiving insulin supplementation for correction of hyperglycemia (BG > 140 mg/dL) compared to those without insulin supplementation except for correction of severe hyperglycemia (BG > 260 mg/dL).

Secondary outcomes include differences between treatment groups in any of the following measures: 1) mean BG before meals, bedtime and 3 AM; 2) number of BG within target; 3) number of hypoglycemia (BG < 70 mg/dl); hyperglycemia (BG > 260 mg/dL during the day or BG>350 mg/dl at bedtime); 4) daily dose of insulin; 5) length of hospital stay and mortality; 6) hospital complications (nosocomial infections, pneumonia, bacteremia, respiratory failure, and acute kidney injury [rise of serum creatinine >0.5 mg/dL (or 50%) of baseline value]), 7) hypoglycemia symptom assessment in both groups.

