**IV.d. Basal Bolus Insulin Protocol.**

Patients will be started on basal bolus insulin therapy as previously reported (6; 7; 11; 13). In brief, subjects treated with insulin prior to admission will receive 80% of the outpatient insulin dose. Insulin-naïve patients will discontinue oral agents and will receive a starting total daily dose (TDD) of insulin of 0.4 U/kg/day for BG between 140-200 mg/dL and 0.5 U/kg/day for BG between 201-400 mg/dL. The starting TDD will be 0.3 U/kg/day in patients  $\geq 70$  yrs or with an eGFR < 60 ml/min. Half of TDD will be given as glargine or detemir once daily and half as meal time insulin (aspart or lispro) divided in three equal doses before meals. Insulin dose will be adjusted daily to maintain a fasting and pre-dinner BG between 100-140 mg/dL (6; 7).

Supplement insulin given as aspart or lispro will be given following a “supplemental insulin scale” protocol (6; 7; 27). Patients randomized to Group 1 will receive supplements to correct BG > 140 mg/dL, and those in Group 2 will not receive supplements except for correction of hyperglycemia (BG>260 mg/dL). Corrective doses for bedtime in group 1 will be given for BG > 220 mg/dL.

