**BEDTIME. Give half of Supplemental Sliding Scale Insulin.**

Blood Glucose (mg/dL)	Sensitive	Usual	Resistant
<221	0	0	0
221-260	1	2	4
261-300	2	3	5
301-350	3	4	6
351-400	4	5	7
> 400	5	6	8

The patient's inpatient primary medical or surgical team may change insulin dose at their discretion in the presence of hypoglycemia (BG <70 mg/dL) or severe hyperglycemia (BG >350 mg/dL). In addition, the attending and/or study physician may consider using the total supplemental insulin dose, patient's nutritional intake, and results of BG testing to adjust insulin regimen.

**Blood glucose monitoring.** BG will be measured before each meal, at bedtime and/or 3 AM (or every 6 hours if a patient is not eating) using a glucose meter. In addition, blood glucose will be measured at any time if a patient experiences symptoms of hypoglycemia or if requested by the treating physician. The nursing staff or a research team staff will record all glucose readings in the hospital's blood glucose flow-sheet (electronic chart).

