**BEDTIME. Give half of Supplemental Sliding Scale Insulin**

Blood Glucose (mg/dL)	Sensitive	Usual	Resistant
< 260	0	0	0
261-300	2	3	5
301-350	3	4	6
351-400	4	5	7
> 400	5	6	8

The attending physician may change insulin dose as his/her discretion in the presence of hypoglycemia (BG <70 mg/dL) or severe hyperglycemia (BG >350 mg/dL). In addition, the attending and/or study physician may consider using the total supplemental insulin dose, patient's nutritional intake, and results of BG testing to adjust insulin regimen.

**Blood glucose monitoring.** BG will be measured before each meal, at bedtime and 3 AM (or every 6 hours if a patient is not eating) using a glucose meter. In addition, blood glucose will be measured at any time if a patient experiences symptoms of hypoglycemia or if requested by the treating physician. The nursing staff or a research team staff will record all glucose readings in the hospital's blood glucose flow-sheet (chart).

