### **VIII. Protection against risks.**

**VIII.a. Hypoglycemia.** We expect that <10% of subjects will experience episodes of hypoglycemia. To minimize the risk, outpatient dose of insulin will be reduced by 20% on admission; and insulin naïve patients  $\geq 70$  years of age and/or with an eGFR  $< 60$  will be started at a TDD of 0.3 U/kg/day.

**VIII.b. Severe hyperglycemia.** Patients with persistent hyperglycemia ( $\geq 3$  consecutive BG readings  $> 260$  mg/dL or a mean daily BG  $\geq 260$  mg/dL) after the 1st day of treatment will be considered as treatment failure and will be switched to continuous insulin infusion if needed. Patients randomized to group 1 will receive insulin supplements for BG  $> 140$  mg/dL. Those randomized to group 2 will receive insulin supplements only when BG  $> 260$  mg/dL. We anticipate that less than 1% of patients will experience severe hyperglycemic episodes (BG  $> 350$  mg/dL).

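### For patients who eat, the 3 AM glucose check can be omitted in Group 1 but is scheduled in Group 2; this is probably a drafting slip, but as written it could make overnight readings differ by arm

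*Combined protocol and SAP*

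**What the plan says.** Section IV.d describes each arm separately, and each description ends with a paragraph on glucose monitoring.

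- Group 1 (corrections above 140 mg/dL): "BG will be measured before each meal, at bedtime and/or 3 AM (or every 6 hours if a patient is not eating".
- Group 2 (corrections only above 260 mg/dL): "BG will be measured before each meal, at bedtime and 3 AM (or every 6 hours if a patient is not eating".

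The six-hourly rule for patients who are not eating is the same in both. Both paragraphs also add that "blood glucose will be measured at any time if a patient experiences symptoms of hypoglycemia", or when the treating physician asks for it.

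In Group 1 the bedtime value is needed for dosing: "Corrective doses for bedtime in group 1 will be given for BG > 220 mg/dL".

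Section IV.b relies on the overnight reading in three places. The primary outcome there is mean daily glucose ("The primary outcome of the study is to compare differences in mean daily BG levels between patients receiving insulin supplementation"). The first secondary outcome is "1) mean BG before meals, bedtime and 3 AM". The third includes the number of readings below 70 mg/dL. Section VII instead names mean fasting glucose as the primary endpoint, and the 18 mg/dL margin and the sample size are stated for that.

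**The concern.** A between-arm comparison of glucose values assumes that both arms are measured on the same schedule. Here the two sentences differ in a single connective, and that changes what staff are told to do overnight.

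Less hypoglycemia without routine corrections is part of the trial's rationale. A symptom-free low at 3 AM is found only if someone checks, and symptom-triggered testing will not reliably pick it up. If Group 1 is checked less often at that hour, its count of lows and its 3 AM mean rest on less complete data. Its mean daily glucose also averages a different set of clock times.

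The difference can affect treatment as well as measurement. Section IV.f requires carbohydrate or dextrose for any reading below 70 mg/dL, and the adjustment rules in section IV.d cut the total daily dose by 20% after an unexplained low. Unequal checking could therefore lead to unequal dosing.

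**Working it through.** **Which reading is optional.** Read literally, the Group 1 connective also allows 3 AM without bedtime. But the Group 1 bedtime scale cannot be applied without a bedtime value, so in practice 3 AM is the reading that can be dropped. For patients who eat, scheduled readings are 3 meals + bedtime = 4, or 5 with 3 AM, in Group 1, against 3 + 1 + 1 = 5 in Group 2. No other section sets one schedule for both arms or says which readings enter mean daily glucose.

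**Sample size, to confirm it is untouched.** Section VII gives margin 18 mg/dL, SD 50 mg/dL, one-sided 0.025, 80% power and 123 per group. The normal approximation gives n = 2 × (1.960 + 0.842)² × 50² / 18² = 121.1, so 122. The noncentral t gives power 0.7997 at 122 and 0.8029 at 123, so 123 is reproduced. No input involves the 3 AM reading.

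**Illustrative size.** The quantities f, s, k and d below are assumptions; the documents give none of them.

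*Mean daily glucose.* Let M be the mean of the other four readings, d the amount by which the 3 AM value lies below M, and f the share of 3 AM checks omitted in Group 1.

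- Group 2 day mean: (4M + (M − d))/5 = M − d/5.
- Group 1 day mean, on average: M − (1 − f)d/5.
- Difference, Group 1 minus Group 2: f × d/5.

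| d (mg/dL) | f = 0.5 | f = 1 |
|---|---|---|
| 0 | 0 | 0 |
| 10 | 1 | 2 |
| 20 | 2 | 4 |
| 30 | 3 | 6 |

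The largest entry is 6/18 = 33% of the margin, but that margin is stated for fasting glucose, so the ratio gives scale only. If 3 AM values run lower than the rest, the shift favors Group 2; if higher, it goes against Group 2.

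*Hypoglycemia, detection only.* Let b be the true share of patients affected, equal in both arms, and s the share of those who are low only at 3 AM and without symptoms. Let k be the number of nights on which such a patient is low, with omissions independent between nights. The share observed in Group 1 is b × (1 − f^k × s). I take b = 12%, the lower figure in section II ("hypoglycemia occurs in 12% and 33% of general medicine and surgery patients treated with basal bolus insulin regimens"), and b = 10%, the ceiling in section VIII.a ("We expect that <10% of subjects will experience episodes of hypoglycemia").

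| b | f, k | s = 0.1 | s = 0.2 | s = 0.3 |
|---|---|---|---|---|
| 12% | 1, any | 10.8% | 9.6% | 8.4% |
| 12% | 0.5, 1 | 11.4% | 10.8% | 10.2% |
| 12% | 0.5, 2 | 11.7% | 11.4% | 11.1% |
| 10% | 1, any | 9.0% | 8.0% | 7.0% |
| 10% | 0.5, 1 | 9.5% | 9.0% | 8.5% |
| 10% | 0.5, 2 | 9.75% | 9.5% | 9.25% |

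Patients missed out of 125 (125 × b × f^k × s, with k = 1):

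- always skipped: 1.5 to 4.5 at 12%, and 1.25 to 3.75 at 10%;
- skipped half the time: 0.75 to 2.25 at 12%, and 0.6 to 1.9 at 10%.

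Results scale in proportion to b. At the 33% also given in section II, always skipping would give 0.33 × 0.9 = 29.7% down to 0.33 × 0.7 = 23.1%. If s = 0 or f = 0, nothing is missed.

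**Response to a detected low.** The table treats a check as pure detection. Under the protocol, a low found in Group 2 is treated, and an unexplained one also reduces that patient's insulin by 20%, which may prevent later lows. The same low missed in Group 1 prompts neither. Detection raises the Group 2 count; the dose cut lowers it afterwards. The documents do not allow the two to be netted.

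**The case against.** The strongest reply is that this is loose copying and not a design feature. Listing 3 AM glucose as a between-group outcome presupposes the reading in both arms. Section X speaks of intensified monitoring for all subjects. The arm sections differ elsewhere in ways that look accidental: a generic drug name in one and a brand name in the other, liraglutide listed only for Group 1, and the half-basal, half-mealtime split missing for previously insulin-treated Group 2 patients although the general text applies it to everyone. Moreover, the Group 1 wording permits both readings and tells nobody to skip one. All of this stands, and practice may have been identical in both arms. It does not remove the point, because the monitoring sentence is an operative instruction and nothing else overrides it.

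The second reply is that the effect may be negligible. The protocol describes glucose on these regimens as relatively flat through the day, which lends no support to a large 3 AM gap. Patients who are not eating and symptomatic lows are handled alike in both arms. This also stands.

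Three stronger readings are tempting, and the documents do not support them.

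- *Group 1 was deliberately monitored less.* No reason for that is given, and the outcome list points the other way.
- *Extra checking can only count against Group 2, so it could never produce a false benefit.* The treatment and dose cut after a detected low may reduce later lows in Group 2, and section IV.b specifies the number of lows.
- *Up to a third of the non-inferiority margin is at risk.* That needs an assumed 30 mg/dL gap, every Group 1 check skipped, and a margin borrowed from a different endpoint.

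**Conclusion.** The inconsistency is real and probably unintended. As written, 3 AM glucose, symptom-free overnight lows and mean daily glucose could be ascertained differently by arm, and dosing could follow. The size is unknown and possibly zero: every figure above depends on assumed skip rates, 3 AM gaps and shares of silent lows. The net direction is indeterminate, for mean daily glucose because the sign of the 3 AM gap is not given, and for hypoglycemia because detection and the dose response pull in opposite directions.

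The sample size is unaffected. The fasting glucose endpoint in section VII is not directly affected; it could be reached only indirectly, through treatment of detected lows and dose changes. The point warrants correction because it concerns named outcomes and costs little to remove, not because a material bias has been shown.

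**What to change.** Use the Group 2 monitoring sentence in both arms: a reading before each meal, at bedtime and at 3 AM, or six-hourly for patients who are not eating. Once the schedules match, this point requires no further change to the analysis.

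If data were already collected under the current text, report the completeness of 3 AM readings by arm, and add a sensitivity analysis of mean daily glucose and hypoglycemia that excludes 3 AM readings from both arms. Both paragraphs require readings to be charted, so the information should be available. This analysis can show whether the measured contrast depends on the 3 AM values; it cannot undo any dose changes those values prompted.

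The cost is one protocol sentence and at most one extra finger-stick per Group 1 patient-day. For data already collected, add a line or two of analysis text and minor programming. The sample size does not change.

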## **Group 2. Basal Bolus insulin regimen without corrective doses of rapid-acting insulin prior to meals**

### **Patients Treated with Insulin Prior to Admission**

- Subjects receiving insulin therapy will receive 80% of the total outpatient insulin dose. For subjects receiving glargine, detemir, regular, lispro, glulisine or aspart, the total daily insulin dose prior to admission will be switched to basal insulin (glargine or detemir) and meal time insulin (aspart/lispro) combination on a unit-for-unit basis.
- Basal insulin (glargine or detemir) will be given once daily, at the same time of the day.
- Patients will receive the full-dose of basal insulin (glargine or detemir) (even if NPO) the day of surgery or diagnostic procedure(s).
- Meal time insulin (aspart/lispro) will be given in three equally divided doses before each meal. To prevent hypoglycemia, if a subject is not able to eat, the dose of aspart/lispro will be held.

### **Patients Treated with Oral Agents Prior to Admission**

- Oral antidiabetic drugs (sulfonylureas, repaglinide, nateglinide, metformin, Actos, DPP4 inhibitors) and non-insulin injected antidiabetic drugs (pramlinitide, exenatide) will be discontinued on admission.
- **Starting total daily insulin dose:**
  - 0.4 units per kilogram of body weight per day when the admission and/or blood glucose concentration at randomization is between 140-200 mg/dL
  - 0.5 units per kilogram of body weight per day when the admission and/or mean blood glucose concentration is between 201-400 mg/dL
  - The starting insulin TDD will be reduced to 0.3 units per kg in patients  $\geq 70$  years of age and/or with an eGFR  $< 60$  ml/min.
- Half of total daily dose will be given as basal insulin (glargine or detemir) and half as meal time insulin (aspart or lispro).
- Basal insulin (glargine or detemir) will be given once daily, at the same time of the day.
- Patients will receive the full-dose of basal insulin (glargine or detemir) (even if NPO) the day of surgery or diagnostic procedure(s).
- Meal time insulin (aspart/lispro) will be given in three equally divided doses before each meal. To prevent hypoglycemia, if a subject is not able to eat, the dose of aspart/lispro will be held.

**Supplemental insulin.** Aspart or lispro insulin will be administered following the “supplemental insulin scale” protocol before meals.

- If a patient is able and expected to eat all or most of his/her meals, supplemental (aspart or lispro) insulin will be administered before each meal following the “usual” dose of the supplemental insulin scale.
- If a patient is not able to eat, supplemental (aspart/lispro) insulin will be administered every 6 hours following the “sensitive” dose of the supplemental insulin scale protocol.

**Insulin adjustment.** Daily insulin dose will be adjusted as follow:

- If the fasting and/or pre-dinner BG is between 100 - 140 mg/dL in the absence of hypoglycemia the previous day: no change
- If the fasting and/or pre-dinner BG is between 140 - 180 mg/dL in the absence of hypoglycemia: increase basal insulin by 10% every day
- If the fasting and/or pre-dinner BG is >180 mg/dL in the absence of hypoglycemia the previous day: increase basal insulin dose by 20% every day
- If the fasting and/or pre-dinner BG is between 70 - 99 mg/dL in the absence of hypoglycemia: decrease basal and prandial insulin TDD by 10% every day
- If a patient develops unexplained hypoglycemia (BG <70 mg/dL), the basal and prandial TDD insulin should be decreased by 20%.

**Insulin supplementation (aspart or lispro) prior to meals:**

**BEFORE MEAL, Supplemental Sliding Scale (number of units) - Add to scheduled insulin dose.**

Blood Glucose (mg/dL)	Sensitive	Usual	Resistant
< 260	0	0	0
261-300	5	6	10
301-350	6	8	12
351-400	7	10	14
> 400	8	12	16

**BEDTIME. Give half of Supplemental Sliding Scale Insulin**

Blood Glucose (mg/dL)	Sensitive	Usual	Resistant
< 260	0	0	0
261-300	2	3	5
301-350	3	4	6
351-400	4	5	7
> 400	5	6	8

The attending physician may change insulin dose as his/her discretion in the presence of hypoglycemia (BG <70 mg/dL) or severe hyperglycemia (BG >350 mg/dL). In addition, the attending and/or study physician may consider using the total supplemental insulin dose, patient's nutritional intake, and results of BG testing to adjust insulin regimen.

**Blood glucose monitoring.** BG will be measured before each meal, at bedtime and 3 AM (or every 6 hours if a patient is not eating) using a glucose meter. In addition, blood glucose will be measured at any time if a patient experiences symptoms of hypoglycemia or if requested by the treating physician. The nursing staff or a research team staff will record all glucose readings in the hospital's blood glucose flow-sheet (chart).

**IV.f. Inpatient Hypoglycemia Management:**

For blood glucose < 70 mg/dL, follow hypoglycemia orders below:

- If patient is alert and can tolerate oral intake, give 20 grams of fast-acting carbohydrate (6 oz. fruit juice or regular soda, crackers).
- If patient not alert and CANNOT tolerate oral intake, give 1 ampule (50 mL) of D50.
- Check finger-stick BG q 15 minutes and repeat above treatment until BG > 100 mg/dL.
- Once BG > 100 mg/dL, repeat finger-stick BG 1 hour later and treat as follows:
  - If BG < 70 mg/dL, call MD and follow Hypoglycemia Orders (above)
  - If BG 70 – 100 mg/dL, give snack/scheduled meal and recheck BG q 1 hr until BG > 100 mg/dL.
  - If BG > 100, no further treatment needed.

**IV.g. Treatment recommendations at discharge.** Treatment of diabetes at discharge will not be part of the current research proposal; however, the following guide based on admission HbA1c will be shared with primary team to help guiding outpatient insulin therapy:

- **Admission A1C < 7% prior to admission:**
  - Discharge on same pharmacologic regimen (oral agents, insulin therapy).
  - Assure there are no contraindications to oral agents (i.e., TZDs and heart failure; metformin and renal failure).
- **Admission A1C between 7% and 10% prior to admission:**
  - Discharge on once daily basal insulin (glargine or detemir) insulin.
  - If no contraindications to oral agents restart oral agents in addition to basal insulin (glargine or detemir) at 50% to 80% of total daily hospital dose.
  - Patients not to be treated with oral agents should be instructed to continue taking 100% of inpatient daily dose of glargine (as monotherapy).
- **Admission A1C ≥ 10% prior to admission:**
  - Discharge on basal bolus regimen at same inpatient total daily insulin dose.
    - Basal insulin (glargine or detemir) once daily, at the same time of the day.
    - Rapid-acting insulin (aspart/lispro) before meals.
  - Alternative: If no contraindications to oral agents (i.e., TZDs and heart failure; metformin and renal failure) restart oral agents in addition to glargine or detemir once daily at 80% of total daily hospital dose.

## **V. METHODS and PROCEDURES APPLIED to HUMAN SUBJECTS:**

**V.a. Subject Population/Inclusion Criteria.** We plan to study a total of 250 male and female patients with a known history of T2DM for >3 months, age 18-80 yr, treated with either diet alone, any combination of oral antidiabetic agents, non-insulin injectables or insulin therapy. Subjects must have a BG >140 mg and <400 mg/dL without laboratory evidence of diabetic ketoacidosis (28).

**Exclusion Criteria.** Subjects with hyperglycemia without a history of diabetes, acute critical illness admitted to the ICU or expected to require ICU admission; receiving continuous insulin infusion, clinically relevant hepatic disease, corticosteroid therapy, creatinine  $\geq 3.5$  mg/dL and/or GFR <30, subjects unable to sign consent, and pregnancy which will be excluded by a urine pregnancy test.

**V.b. Study Sites:** The study will be conducted at Grady Memorial Hospital and Emory University Hospitals (EUH and EUHM).

## **VI. CLINICAL MANAGEMENT GUIDELINES**

**V.I.a. Treatment of Hypoglycemia.** Hypoglycemia, defined as a BG level < 70 mg/dL will be treated following standard hypoglycemia protocols available at our institutions (6; 7; 29).

**V.I.b. Assessment and Monitoring of Hospital Complications and Mortality.** The research team will follow patients daily in order to determine presence of infectious and non-infectious complications. Nosocomial infections will be diagnosed based on standardized CDC criteria (30).

**VII. Data Analysis.** The primary endpoint of this study is mean fasting BG concentration between treatment groups. We set the equivalence margin in our non-inferiority hypothesis for comparing treatment effect as 18 mg/dL (1 mmol/l). Based on previous studies (6; 7), we anticipate a standard deviation of mean fasting BG~50 mg/dL. With a one-sided, two-sample t-test, 123 subjects would be required for each group to achieve 80% power to detect non-inferiority. Here we conservatively set the significance level as 0.025 to ensure sufficient power when a two-sided test is used for the primary outcome, we will perform cross-sectional analyses using one-way ANOVA or linear models, followed by repeated measures ANOVA or linear models to estimate difference between treatment groups while simultaneously examining mean fasting BG across multiple days during treatment. Similar analyses will be conducted for continuous secondary outcomes. Chi-square tests (or Fisher's Exact test), Logistic regression, and Poisson regression will be conducted to analyzed discrete secondary outcomes. A p-value of <0.05 is considered significant. We expect a very low attrition rate in the proposed study. Therefore, a total of 250

patients (125 patients per group) will be recruited in this pilot study. The proposed methods will be implemented by SAS (v9.2).

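### Section IV.b makes mean daily BG the primary outcome, section VII makes mean fasting BG the primary endpoint, and nothing says which governs

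*Combined protocol and SAP*

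**What the plan says.** Section IV.b (Primary and Secondary Outcomes) states: "The primary outcome of the study is to compare differences in mean daily BG levels between patients receiving insulin supplementation". The first item in its secondary list is "mean BG before meals, bedtime and 3 AM". Fasting BG is not listed there under its own name.

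Section VII (Data Analysis) opens: "The primary endpoint of this study is mean fasting BG concentration between treatment groups". The sample-size inputs follow:

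- **Margin:** 18 mg/dL, in the sentence straight after the endpoint is named.
- **SD:** "we anticipate a standard deviation of mean fasting BG~50 mg/dL".
- **Test:** one-sided two-sample t-test at 0.025.
- **Result:** "123 subjects would be required for each group to achieve 80% power to detect non-inferiority", rounded up to 125 per group.

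The analysis text then says "for the primary outcome, we will perform cross-sectional analyses using one-way ANOVA or linear models". The repeated-measures step that follows works "while simultaneously examining mean fasting BG across multiple days during treatment". Continuous secondary outcomes get similar analyses.

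No section separates the terms primary outcome and primary endpoint, calls the two variables co-primary, gives an order of testing, or says which section prevails.

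**The concern.** Mean daily BG and mean fasting BG are different variables. A fasting value is one reading a day, whereas a daily mean also takes in later readings. The protocol's own preliminary data on the bedtime-correction study report fasting glucose and mean daily glucose as separate results.

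The two may also respond differently to this intervention. By the supplemental tables under IV.d, the arms differ before meals over roughly 141 to 260 mg/dL, but at bedtime only over 221 to 260 mg/dL. A daytime effect could therefore show in the daily mean and less in the fasting value. That is an inference and is not stated in the documents.

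An analyst following VII and an author following IV.b would report different primary results, each in line with the protocol. The non-inferiority conclusion therefore rests on a choice that the plan leaves open, possibly until data are available. The stated 80% power also cannot be quoted for the outcome that IV.b calls primary.

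**Working it through.** **1. The plan's own figure.** Inputs from section VII: margin 18, SD 50, one-sided 0.025, 80% power, true difference 0.

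- Normal approximation: n = 2 × [50 × (1.960 + 0.842) / 18]² = 121.1, so 122 per group.
- Exact t: the noncentrality is 18 / (50 × √(2/n)). At n = 122 it is 2.812 and power is 79.97%. At n = 123 it is 2.823 and power is 80.3%. At n = 125 it is 2.846 and power is 80.9%.

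The stated 123 is the exact-t answer, so the arithmetic is right for fasting BG.

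**2. Power for mean daily BG at 125 per group.** The documents give no planning SD. The only mean daily SDs are background results of the earlier general-surgery trial (Preliminary Data): 32 mg/dL with basal bolus and 47 mg/dL with sliding scale. I take these as between-patient SDs and assume the same 18 mg/dL margin.

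| Daily SD | Standard error, SD × √(2/125) | 18 / standard error | Power | n per group for 80% |
|---|---|---|---|---|
| 32 | 4.05 | 4.45 | 99.3% | 51 |
| 47 | 5.95 | 3.03 | 85.5% | 108 |

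Power at 125 per group stays at about 80% or more up to a daily SD of about 50.6. The basal bolus arm (SD 32) is the closer analogue, since both arms here receive basal bolus insulin.

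**3. A correlation consistent with those SDs.** Let the daily mean average k readings, fasting among them, each with SD s and pairwise correlation r. Its variance is s²(1 + (k − 1)r)/k, and its covariance with the fasting reading is the same quantity. The correlation is therefore SD(daily) / s. With s = 50:

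- daily SD 32 gives 32/50 = 0.64
- daily SD 47 gives 47/50 = 0.94

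**4. How often the two endpoints disagree.** I simulated 400,000 trials per setting, with 125 per group, both true differences 0, and each endpoint tested against 18 mg/dL at one-sided 0.025.

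| Daily SD, correlation | Disagree | Fasting misses, daily meets | Fasting meets, daily misses |
|---|---|---|---|
| 32, 0.64 | 18.6% | 18.5% | 0.1% |
| 47, 0.94 | 7.8% | 6.2% | 1.7% |

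**5. Error rate if either endpoint could win (hypothetical).** The plan states no such rule. With both true differences exactly at the margin, the one-sided error is 0.025 + 0.025 − P(both succeed). From the bivariate normal this is 0.043 at correlation 0.64 and 0.033 at 0.94, against the planned 0.025.

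**The case against.** The strongest reply is that section VII settles the matter. It names its endpoint in the first sentence, and the margin, SD, sample size and repeated-measures clause all follow from it. The primary outcome mentioned later in that paragraph is most naturally the variable just defined. This stands: VII is a complete plan for fasting BG, and a reader who infers that it is incoherent within itself goes too far. It does not remove the conflict, because IV.b is the section that defines the outcomes and it says otherwise.

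Several stronger readings are tempting but not supported:

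- **The trial is underpowered for mean daily BG.** The documents' own SDs point the other way, given the same margin.
- **The 18.6% disagreement is a new hazard of that size.** At daily SD 32 nearly all of it is the planned type II error for fasting BG (100 − 80.9 = 19.1%). It reflects unequal precision of the two endpoints.
- **The type I error is inflated.** That needs an either-endpoint rule, or a choice made after seeing the data. Neither is in the plan, and each section names only one primary.
- **IV.b expressly demotes fasting BG to secondary.** It does not name it. The pre-breakfast value plausibly falls under the pre-meal means, but section IV.c uses fasting and pre-meal BG as separate terms.

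Sections IV.a and VII also call the study a pilot. That lowers the stakes somewhat, but VII still sets a margin, an alpha level and 80% power for a non-inferiority test, and such a test needs one named variable.

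**Conclusion.** The contradiction is real and must be fixed. Two current sections name different primary variables, and following the plan exactly yields two primary results. The outcome named in IV.b has no planning SD or power statement. The sample size is correct for fasting BG, and no shortfall is shown for mean daily BG.

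The size of the problem is the chance that the choice changes the conclusion: about 18.6% of trials at daily SD 32 and about 8% at daily SD 47 when there is no true difference on either endpoint. These figures assume a common 18 mg/dL margin, SDs carried over from one surgical trial, and equally variable readings within the day. The contradiction itself rests on none of these assumptions.

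**What to change.** Name one primary endpoint in the same words in IV.b and VII, and make the other secondary. The choice is the sponsor's. It should be made before those choosing see any comparison by arm. That wording matters because the monitoring committee reviews data, including efficacy, at 6-month intervals.

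For the chosen endpoint, state the SD, the margin and the resulting power at 125 per group, and name that variable in both the cross-sectional and the repeated-measures model.

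If mean daily BG is chosen, also define which readings enter it, identically for both arms. The monitoring paragraphs under IV.d differ: for Group 1 bedtime and 3 AM are joined by and/or, for Group 2 by and. They must be reconciled, or the daily mean could be built from different readings in each arm.

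The cost is wording in two sections and one power sentence, plus a definition of readings if the daily mean is chosen. On the documents' SDs no patients are added: 80% power needs 123 per group for fasting BG, and 51 or 108 for mean daily BG with the same margin, against 125 planned.
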